6 OVERALL STUDY DESIGN AND PLAN

6.1 **Study rationale**

6.1.1 **Rationale for administered radioactivity doses**

For ^{68}Ga -PSMA, we will use the administered radioactivity dose ranges described in the literature. The administered dose may vary between 110 – 370 MBq (equivalent range of 3.0 – 7.0 mCi). The amount of radioactivity per subject is in accordance with the radiation protection principle “as low as reasonably achievable (ALARA)”, whilst ensuring image quality that is suitable for the planned analyses ^{18,20}.

6.2 **Study timeframe**

The recruitment period for the study is expected to last up to 4 years. The duration of patient participation in this study will end with the clinically indicated biopsy procedure.

6.3 **Risks and benefits to subjects**

There are no expected direct benefits to subjects who participate in this trial. However, participants may benefit under certain conditions. First, if targeted biopsies identify a significant prostate cancer lesion not identified on standard biopsies or MRI, the patient would potentially benefit from the detection of such disease. Second, patients who will undergo subsequent definitive treatment may benefit if imaging identifies aggressive features such as extraprostatic spread or nodal metastases that otherwise would not have been identified. Also, the treatment team will be notified about the study imaging results in case of any other unexpected relevant abnormal findings. Accordingly, treatment decisions can be made on the basis of ^{68}Ga -PSMA scan results.

The risks to subjects mainly relate to the procedures employed for i.v. injection of the investigational radiotracers. Also, there are risks due to the placement of an i.v. catheter for drug injections as intravenous injections as well as small amounts of blood withdrawn. These are known to carry a small risk of infection and hematoma (infrequently occurring). There is also a small increase in risk due to additional prostate biopsy cores obtained with the clinically indicated prostate biopsy procedure. This risk is limited as we will not select more than 2 additional lesions for targeting.

As the study will be performed as a microdosing study, risks concerning the tracer mass are not to be expected. All subjects will be subject to small amounts of research-related ionizing radiation.

There is also a possibility of breach of confidentiality.

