8 TREATMENT OF SUBJECTS

In nuclear medicine imaging, it is important to record sufficient numbers of (true) positron annihilation events in VOIs in order to produce images of good quality, which can reliably be interpreted and deliver reproducible results. The number of recorded events increases with the duration of the acquisition period. Furthermore, for a given duration of image acquisition and for a given imaging time post injection, image quality increases with the administered radioactivity over a wide range of radioactivity doses. Therefore, the injected radioactivity should be high in order to obtain good images. On the other hand, higher radioactivity doses cause higher radiation exposure to the subjects, which is to be avoided. The optimum radioactivity dose is defined as the lowest dose that provides high image quality for a given duration of image acquisition and for a defined imaging time post injection.

8.1 ^{68}Ga -PSMA

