8.1.2 Treatment administration

The amount of ^{68}Ga -radioactivity administered for a single study will range between 3.0 and 7.0 mCi.

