9 TREATMENT PERIOD

Informed consent will be obtained. All subjects must satisfy one inclusion criterion and none of the exclusion criteria listed. Signed and dated informed consent must be obtained from all subjects before any study-specific procedures are performed. The consent document may be sent to a potential participant prior to obtaining consent for their information. A screening visit will be performed within 2 months before radiotracer administrations, however can be performed on the day of PET/CT imaging. Subjects will be permitted to continue taking any routine or necessary medication.

The following data will be collected on study-specific CRFs.

- Date of birth
- Weight
- Height
- Concurrent medications
- Medical history and concurrent diseases
- Report and date of most recent histological tissue evaluation from any known prostate cancer
- Results of screening tests

Personal data (including contact information) will be collected with the subject's permission and only to the extent that is necessary for the purposes of the study.

Vital signs (pulse, respirations, systolic and diastolic blood pressure) are recorded. A cannula (or indwelling catheter) will be placed into a vein, preferably in the antecubital region, for tracer administration.

The injection site will be examined for any abnormal findings before dosing. In the interests of comfort, subjects will be advised to empty their bladder and, if necessary, complete a bowel movement before being positioned on the scanner table.

9.1 ⁶⁸Ga-PSMA PET/CT

a) ⁶⁸Ga-PSMA-11 PET preparation and injection:

The injected dose will be 111-259 MBq (3-7 mCi) of ⁶⁸Ga-PSMA-11 PET. PET imaging will begin 50-100 minutes after injection. Scan time per bed position will be determined based on expected count statistics related to the administered dose.

b) Patient preparation: no fasting is required.

c) PET protocol: Scan coverage will extend from mid-thigh to the base of the skull, starting from the mid-thighs to prevent urinary bladder radiotracer accumulation at the start of PET imaging. Scan time per bed position will be determined based on expected count statistics, which is determined mainly by the administered dose. Scan time will therefore be between 15 and 40 minutes. In certain circumstances, coverage may be extended to the toes. Contrast may be administered as needed.

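### Section 6.1.1 equates 110–370 MBq with 3.0–7.0 mCi, but 370 MBq is 10.0 mCi and 7.0 mCi is 259 MBq, so one sentence sets two upper activity limits

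*Combined protocol and SAP*

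**What the plan says.** The combined protocol and SAP states the administered activity in four places.

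- **Section 1, Synopsis, Dose row:** 3.0 to 7.0 mCi, with no MBq figure.
- **Section 6.1.1, Rationale for administered radioactivity doses:** "The administered dose may vary between 110 – 370 MBq (equivalent range of 3.0 – 7.0 mCi"). The paragraph attributes the range to published experience and says that the activity per subject respects the ALARA principle.
- **Section 8.1.2, Treatment administration:** "radioactivity administered for a single study will range between 3.0 and 7.0 mCi", again with no MBq figure.
- **Section 9.1, ⁶⁸Ga-PSMA PET/CT:** "The injected dose will be 111-259 MBq (3-7 mCi").

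Two of the four, 6.1.1 and 9.1, give a range in MBq. That is the unit in which the List of Definitions in section 3 expresses radioactive dose. The introduction to section 8 adds the general consideration that "higher radioactivity doses cause higher radiation exposure to the subjects, which is to be avoided".

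**The concern.** Section 6.1.1 presents its MBq and mCi ranges as the same range in two units. The lower ends match to rounding, but the upper ends cannot both be right. The two places that state an MBq limit also disagree with each other: 370 MBq in 6.1.1 and 259 MBq in 9.1.

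The upper limit on activity bears on how much radioactivity a subject may receive and on whether a given injection complied with the protocol. Section 8.5 requires the injected activity to be checked and recorded. Section 10.1 has deviations discussed at study-team meetings at least every three months. Section 12.3 lets the principal investigator exclude subjects or individual values after a protocol violation. Each of these needs one limit to check against. Section 7.3 also allows a subject to take part again and receive a repeat scan, so the ambiguity can apply more than once to the same person.

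**Working it through.** **Inputs**

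| Place | MBq range | mCi range |
|---|---|---|
| Synopsis | not given | 3.0–7.0 |
| 6.1.1 | 110–370 | 3.0–7.0 |
| 8.1.2 | not given | 3.0–7.0 |
| 9.1 | 111–259 | 3–7 |

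**Step 1. Conversion factor.** By definition 1 mCi is 37 MBq. Section 9.1 gives the same factor, so no outside figure is needed:

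- lower end: 111 / 3 = 37.0 MBq per mCi
- upper end: 259 / 7 = 37.0 MBq per mCi

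**Step 2. Factors implied by section 6.1.1.**

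- lower end: 110 / 3.0 = 36.7 MBq per mCi
- upper end: 370 / 7.0 = 52.9 MBq per mCi

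If the two ranges were equivalent, the two factors would agree. They do not, and the upper one is far from 37. The equivalence stated in 6.1.1 is not reproduced.

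**Step 3. Convert each end of 6.1.1 at 37 MBq per mCi.**

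- 110 / 37 = 2.97 mCi, and 3.0 × 37 = 111 MBq
- 370 / 37 = 10.0 mCi, and 7.0 × 37 = 259 MBq

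**Step 4. Could rounding explain it?** Take the mCi figures as rounded to one decimal place.

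- 3.0 mCi covers 2.95 to 3.05 mCi, which is 109.2 to 112.9 MBq. The figure 110 lies inside.
- 7.0 mCi covers 6.95 to 7.05 mCi, which is 257.2 to 260.9 MBq. The figure 370 lies well outside.

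The lower end is rounding (a gap of 1/111 = 0.9%). The upper end is not.

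**Step 5. Size of the discrepancy at the upper end.**

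- difference: 370 − 259 = 111 MBq, or 111 / 37 = 3.0 mCi
- ratio: 370 / 259 = 10 / 7 = 1.43

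**Step 6. What the text says about an injection between 259 and 370 MBq (7.0 to 10.0 mCi).**

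| Statement of the range | Inside or outside |
|---|---|
| 6.1.1, MBq figure | inside |
| 6.1.1, mCi figure | outside |
| Synopsis | outside |
| 8.1.2 | outside |
| 9.1, both units | outside |

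**The case against.** The best defence is that this is one stray figure in a rationale section. The wording there is permissive, whereas 8.1.2 and 9.1, which govern the injection itself, use directive wording and agree with each other and with the synopsis. Staff working from those sections meet a single range, so the practical ambiguity is small. The documents also give no effective or organ dose, so the discrepancy is in administered activity and not in a stated exposure ceiling. Nor does section 6.1.1 derive its upper limit from ALARA; it takes the range from the literature and then says that the activity respects that principle.

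Much of this is fair. The figure of 370 MBq is isolated, the point is best described as one about the upper activity limit, and nothing in the plan suggests that injections above 259 MBq are expected. But agreement elsewhere does not remove the contradiction. Section 6.1.1 belongs to the study design chapter, states a permitted range, and does so in the protocol's defined unit for radioactive dose. Because it cites literature ranges, the documents leave open whether 370 MBq is a slip or a wider range that was converted wrongly. A count of which figure appears more often does not settle that. The objection limits the practical weight of the point but leaves the error standing.

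**Conclusion.** The concern holds. Section 6.1.1 is wrong as written: its upper MBq and mCi figures differ by 111 MBq (3.0 mCi), a ratio of 1.43, and its MBq limit contradicts section 9.1. The conclusion rests only on the fixed conversion of 37 MBq per mCi, which section 9.1 itself uses. The lower-end difference is rounding and needs no comment beyond tidying. The error has no bearing on the sample size, the primary analysis or the design. What it affects is the stated upper limit on administered activity and the classification of any injection above 259 MBq. The documents do not show which upper limit was intended, and this review takes no position on that. It should be corrected, because it concerns radioactivity given to subjects and correction is simple.

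**What to change.** The sponsor should confirm the intended range and state it identically, in both MBq and mCi, in the synopsis and in sections 6.1.1, 8.1.2 and 9.1. The lower end should be aligned at the same time so that 110 and 111 MBq do not both appear. The confirmed limit should then be the one used when recorded activities are checked for deviations.

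The synopsis, 8.1.2 and 9.1 already agree with one another, so the number of sections whose limit must change depends on the sponsor's answer. Between one and four sections are affected. The cost is text reconciliation only, with no change to design, sample size or analysis.

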7 SELECTION AND WITHDRAWAL OF SUBJECTS

7.1 Procedures for enrolment

Subjects will be recruited at Michigan Medicine.

7.2 Inclusion criteria

Male subjects (≥ 18 years of age) with prior mpMRI (within 3 months of recruitment) resulting in at least one PI-RADS 3-5 lesion with clinical need for a prostate biopsy procedure can participate, if one of the 2 criteria apply:

- Known Gleason 6 (3+3) or 7 (3+4, 4+3) prostate cancer undergoing active surveillance or in the confirmation phase of active surveillance,
- or
- Rising PSA with either a) no prior biopsy or b) single or multiple negative prior biopsies.

7.3 Exclusion criteria

Subjects cannot participate in this study if any of the following applies:

- Prostate biopsy within 12 weeks prior to enrollment
- Acute prostatitis within the last 6 months
- Current non-urologic bacterial infection requiring active treatment with antibiotics
- Active other malignancy (except basal cell or squamous cell skin cancer) within the last 2 years
- Body weight greater than 350 lbs (158 Kg)
- Inability or unwillingness to receive a prostate biopsy procedure
- Unable to lie flat, still, or tolerate a PET/CT scan
- Unable to provide own consent
- Concurrent severe and/or uncontrolled and/or unstable medical disease other than prostate cancer (e.g. poorly controlled diabetes, congestive heart failure, myocardial infarction within 6 months prior to study participation, unstable and uncontrolled hypertension, acute renal failure of any intensity, chronic renal or hepatic disease, severe pulmonary disease)
- Prisoner.

Subjects who received a ^{68}Ga -PSMA PET/CT and subsequent (clinical) TRUS-guided targeted biopsy, and are again in clinical need of a prostate biopsy can again take part in the study to receive repeat ^{68}Ga -PSMA PET/CT imaging.

7.4 Withdrawal and termination criteria

7.4.1 Subject withdrawal

There are no formal withdrawal criteria for this study. During the conduct of the study, the investigator will review for signals that would indicate the need for withdrawal of a subject.

In accordance with the Declaration of Helsinki, each subject is free to withdraw from the study at any time. Investigators also have the right to withdraw subjects from the study in the event of illness, AEs, or other reasons concerning the health or well-being of the subject, or in the case of lack of co-operation.

Should a subject withdraw after administration of the radiotracer, or should the investigators decide to withdraw the subject, all efforts will be made to complete and report the protocol-stipulated observations up to the time of withdrawal as thoroughly as possible. A final evaluation at the time of the subject's withdrawal should be made and an explanation given of why the subject is withdrawing or being withdrawn from the study. The reason and date and time of withdrawal must be noted in a case report form (CRF). If the reason for withdrawal is an AE, monitoring will continue until the outcome is established.

7.4.2 Study termination

The principal investigator reserves the right to terminate the study on safety grounds at any time. On termination of the study, the investigators will assure that adequate consideration is given to the protection of enrolled subjects' interests. Termination of the study will be considered in the event of significant adverse safety findings occurring at any time during the performance of the study. Should termination be necessary, the IRB, the local health authority, and any other relevant local or national health authority (FDA) will be notified.

8 TREATMENT OF SUBJECTS

In nuclear medicine imaging, it is important to record sufficient numbers of (true) positron annihilation events in VOIs in order to produce images of good quality, which can reliably be interpreted and deliver reproducible results. The number of recorded events increases with the duration of the acquisition period. Furthermore, for a given duration of image acquisition and for a given imaging time post injection, image quality increases with the administered radioactivity over a wide range of radioactivity doses. Therefore, the injected radioactivity should be high in order to obtain good images. On the other hand, higher radioactivity doses cause higher radiation exposure to the subjects, which is to be avoided. The optimum radioactivity dose is defined as the lowest dose that provides high image quality for a given duration of image acquisition and for a defined imaging time post injection.

8.1 ^{68}Ga -PSMA

8.1.1 Investigational medicinal product preparation

Gallium-68 labeled PSMA-11 (or PSMA-HBED-CC) is a radiopharmaceutical that will be produced under cGMP.

8.1.2 Treatment administration

The amount of ^{68}Ga -radioactivity administered for a single study will range between 3.0 and 7.0 mCi.

8.2 Method of numbering subjects

At screening, subjects will be given screening code numbers (starting from sc001, ect.). Once enrolled, subjects will be assigned unique subject numbers. Subject identification numbers will start from 001 to the maximum recruitment number.

8.3 Blinding

This will be an open-label study and no blinding will be performed.

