9.2.5 Image interpretation and correlation with standard of truth

PET and MR imaging will be assessed visually. Abnormalities found on MRI and ⁶⁸Ga-PSMA PET will be selected as targets for image-guided biopsies.

Once prostate biopsies are obtained, the location of each biopsy is retrospectively associated with a matching region on pre-biopsy imaging (facilitated via image co-registration) and semi-quantitative PET data are obtained and compared with the standard of truth (Gleason score histology). Accordingly, we will determine whether a selected target was true positive, false positive, true negative or false negative on imaging (MRI and ⁶⁸Ga-PSMA PET) relative to pathological proof. Please note that the location (in 3D space) of a given biopsy core is known from ALL biopsies, whether obtained as standard or targeted core. This is possible because the navigated ultrasound workstation (i.e. UroNav, Invivo) used will record the biopsy core location (trajectory and core length within the gland) in 3D for all cores obtained ^{55,56}.

Accordingly, the sensitivity and specificity for the detection of low-grade (Gleason 3+3) and significant PCa (Gleason \geq 3+4) is determined for both modalities, ⁶⁸Ga-PSMA PET (based on uptake measures) and mpMRI (based on PI-RADS scores).

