12.5.2 Analysis of Primary Endpoints

PET images will initially be interpreted by a board certified nuclear medicine physician or a board-certified radiologist experienced in reading PET at the time of the imaging study at Michigan Medicine. Upon request, case report forms and coded ⁶⁸Ga-PSMA PET/CT imaging data will be provided to the FDA for review.

Intraprostatic lesions identified by mpMRI as PI-RADS 3-5 will be graded visually on a two-point scale as either positive or negative for elevated ⁶⁸Ga-PSMA uptake relative to prostatic gland uptake (0=Negative or 1=Positive).

Any focal intraprostatic elevated ⁶⁸Ga-PSMA uptake relative to prostatic gland that was not identified by mpMRI (as PI-RADS 3-5) but was targeted at biopsy will also be evaluated visually as either positive or negative (0=Negative or 1= Positive).

All subjects with histopathology correlates will be analyzed for the primary aim. Sensitivity and specificity, positive and negative predictive values, and accuracy (along with the corresponding two-sided 95% confidence intervals) will be determined on a per-subject and per-lesion basis for ⁶⁸Ga-PSMA-11 PET and mpMRI regarding the detection of Gleason \geq 3+4 cancer. Standard reference of truth is histopathology from all individual biopsy cores, targeted and standard cores.

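### No section masks the image readers or fixes the analysed PET values before histology is known, so they could be set with the Gleason result in view; locking them first needs no extra reader

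*Combined protocol and SAP*

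**What the plan says.** Section 8.3 is one sentence: "This will be an open-label study and no blinding will be performed". It makes no exception for image reading or PET measurement, and no other section adds one.

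The timing of the imaging values is spread over several sections:

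- **PI-RADS.** Section 7.2 requires an mpMRI with a PI-RADS 3-5 lesion before recruitment, so this score precedes the study biopsy.
- **Initial PET read.** Section 12.5.2 says "PET images will initially be interpreted by a board certified nuclear medicine physician or a board-certified radiologist", and places that read at the time of the imaging study.
- **Target review.** Sections 9.2.1 and 9.2.5 have PET and MRI reviewed and targets chosen before biopsy, including PET-positive lesions that mpMRI did not score 3-5.
- **Binary PET grade.** For mpMRI lesions, Section 12.5.2 says "Intraprostatic lesions identified by mpMRI as PI-RADS 3-5 will be graded visually on a two-point scale as either positive or negative". No date or lock is given. For PET-only lesions, the condition is that the lesion "but was targeted at biopsy will also be evaluated visually as either positive or negative", which reads as a step after biopsy.
- **Visual score.** Section 9.3.3 defines a 0-3 uptake score, also undated.
- **Semi-quantitative PET.** Under Section 9.2.5, after biopsy, each core location "is retrospectively associated with a matching region on pre-biopsy imaging (facilitated via image co-registration) and semi-quantitative PET data are obtained". The same section compares these data with Gleason histology and classes each target as a true or false positive or negative.

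The primary model in Section 12 uses PET uptake as a predictor without saying whether this is the binary grade or a measured value.

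**The concern.** The binary grade and the 0-3 score are visual judgements relative to background. The 2 SD positivity threshold in Section 9.2.1 is offered only as what preliminary data suggest. Uptake values depend on which region is matched to a core. A reader who knows that a core was benign, or Gleason 3+4 or higher, can lean towards the matching answer without intending to.

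The exposure is one-sided. Both models share a PI-RADS score that predates the study biopsy; the values still open afterwards are on the PET side. Any such influence would therefore tend to raise the apparent gain of PET/MRI over mpMRI, which is the primary comparison. It cannot be undone at analysis, because a read made before histology was known cannot be recreated later.

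**Working it through.** **Inputs.** From Section 12.1: model (1) sensitivity and specificity are both 0.789; model (2) gains 0.02 in sensitivity and 0.15 in specificity; the stated positive likelihood ratios are 3.74 and 5.02, a difference of 1.28; N = 100 with at least 38 diseased, which leaves 62 negative. From Table 1: 48 diseased and 52 negative.

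**Step 1: the plan's own figures.** LR+ = sensitivity / (1 − specificity).

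- Model (1): 0.789 / 0.211 = 3.74. This reproduces.
- Model (2) with the stated gains: 0.809 / (1 − 0.939) = 0.809 / 0.061 = 13.26. This is not 5.02.
- Specificity that gives 5.02: 1 − 0.809 / 5.02 = 0.839, a gain of 0.05. Check: 0.809 / 0.161 = 5.02.

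The plan thus supports two values for model (2) specificity. They need reconciling as a separate matter; both are carried here.

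**Step 2: how far a few changed reads move LR+.** Assume one read per subject and hold sensitivity at 0.809. With n negative subjects there are n(1 − specificity) false positives. If k of them are re-read as negative, LR+ = 0.809 / [(n(1 − specificity) − k) / n].

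| Specificity | Negatives | False positives | k = 0 | k = 1 | k = 2 | Shift at k = 2 |
|---|---|---|---|---|---|---|
| 0.839 | 52 | 8.372 | 5.02 | 5.71 | 6.60 | 1.58 |
| 0.839 | 62 | 9.982 | 5.02 | 5.58 | 6.28 | 1.26 |
| 0.939 | 52 | 3.172 | 13.26 | 19.4 | 35.9 | 22.6 |

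Examples: 0.809 / (6.372 / 52) = 6.60; 0.809 / (7.982 / 62) = 6.28; 0.809 / (2.172 / 52) = 19.4.

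At specificity 0.839, two changed reads exceed the 1.28 margin with 52 negatives but fall just short of it with 62. With 62 negatives, three changed reads give 0.809 / (6.982 / 62) = 7.18, a shift of 2.16.

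**Step 3: can the order of steps be changed?** Matching cannot come before the cores exist. But Section 9.2.5 says the workstation "will record the biopsy core location (trajectory and core length within the gland) in 3D for all cores obtained". Those coordinates do not depend on the Gleason result, so regions can be placed and measured after biopsy and before histology is linked. The grades of candidate lesions need no coordinates and can be fixed at the target review.

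**The case against.** **The sentence in Section 8.3 may be about dosing.** It stands under treatment of subjects and opens by calling the study open-label. A reader might infer that the plan deliberately forbids masked reading. The documents do not go that far: they state that there is no blinding and are otherwise silent about readers. The silence is enough for the point, and open-label dosing is compatible with reads fixed before histology.

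**Much is already judged before biopsy.** The initial PET read and target selection precede the histology, and PET positivity must be considered to pick PET-only targets. This stands and narrows the exposure. What remains is that nothing makes those judgements the analysed values.

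**Post-biopsy matching is unavoidable, and recorded coordinates limit discretion.** Both are true. A reader might infer from Section 9.2.5 that measurement is made with the Gleason result in hand. The text says only that it follows biopsy, not that it follows the pathology report. The gap is a missing safeguard, not a stated practice.

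**The arithmetic does not measure bias.** This also stands. Any two changed reads, biased or not, move a ratio built on so few false positives. Up to 3 targets per subject and a lesion-level model also mean that one read per subject is a simplification. A reader might infer that two biased reads are enough to produce the 1.28 difference. That fails with 62 negatives and rests on a specificity that Section 12.1 does not state.

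**Conclusion.** The concern holds as a risk. The plan as written permits the analysed PET grade, visual score and uptake values to be set with the Gleason result in view, while PI-RADS is already fixed. Any resulting bias would tend to favour PET/MRI. A reader might go further and conclude that PET accuracy will be inflated; the documents do not support that, because they give no rate at which reads would change.

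The figures show only how sensitive the endpoint is. Two changed false positives move LR+ by 1.26 to 1.58 at specificity 0.839, and a single one of 52 moves it by about 6.1 (13.26 to 19.4) at 0.939. They assume one read per subject, sensitivity held at 0.809, and 52 or 62 negative subjects as stated. The case for change rests on the missing safeguard and its low cost.

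**What to change.** Keep dosing open-label. In Sections 8.3, 9.2.5 and 12.5.2, require that:

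1. the PI-RADS score, the PET 0/1 grade and the 0-3 score of each candidate lesion are dated and locked in the CRF at the pre-biopsy target review;
2. core-to-region matching and uptake measurement are done from the recorded 3D core coordinates, and locked, before Gleason results are linked;
3. the primary analysis uses only the locked values, with any later correction confined to a sensitivity analysis.

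**Cost.** A CRF lock step, and some sequencing so that measurement is finished before the measuring staff open the pathology results. At a single center this is a real, though modest, operational demand. The sample size is unchanged and no procedure is added. That the same readers can do the work is an inference from the existing target review and the recorded coordinates; the plan does not discuss it.

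**What it does not solve.** Men under active surveillance enter with a known Gleason score, and Section 9 collects the latest histology report on the CRF. Locking does not hide those earlier results from the readers.
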